H	DATA HANDLING AND RECORD KEEPING	12
H1	CONFIDENTIALITY AND SECURITY	13
H2	TRAINING.....	13
H3	CASE REPORT FORMS AND SOURCE DOCUMENTS.....	13
H4	RECORDS RETENTION	13
H5	PERFORMANCE MONITORING.....	13
I	STUDY MONITORING, AUDITING, AND INSPECTING	13
I1	STUDY MONITORING PLAN.....	13
I2	AUDITING AND INSPECTING	13
J	STUDY ADMINISTRATION	13
J1	ORGANIZATION AND PARTICIPATING CENTERS.....	13
J2	FUNDING SOURCE AND CONFLICTS OF INTEREST.....	13
J3	COMMITTEES	13
J4	SUBJECT STIPENDS OR PAYMENTS	13
J5	STUDY TIMETABLE	14
K	PUBLICATION PLAN	14
L	ATTACHMENTS	14
L1	TABLES	14
L2	INFORMED CONSENT DOCUMENTS.....	14
L3	PATIENT EDUCATION BROCHURES	14
L4	SPECIAL PROCEDURES PROTOCOLS	14
L5	QUESTIONNAIRES OR SURVEYS.....	14
M	REFERENCES	15

A Introduction

A1 Study Abstract

Auditory training as the potential to dramatically affect older persons' adjustment to a new hearing aid and to maximize the benefits they receive from wearing one. In turn, by wearing hearing aids, they experience easier and more successful communication patterns. They enhance their ability to engage in everyday conversations and will be able to become more socially involved with their family and friends. In this study we will try to determine the extent to which web-based cLEAR auditory brain training, with concomitant support from a cLEAR in-house audiologist, affects satisfaction with new hearing aids and increases daily use time. Thirty adults over the age of 60 years will receive new hearing aids for the first time. After an adjustment period, half will complete cLEAR's auditory brain training program right away and the other half will complete it after a delay period, and both will complete a control condition. To establish the level of feasibility and clinical utility we will measure hearing aid satisfaction, benefit ratings, and hearing aid use time.

A2 Primary Hypothesis

Use of the web-based cLEAR auditory brain training system with concomitant support from a cLEAR in-house audiologist improves satisfaction with new hearing aids and increases daily use time.

A3 Purpose of the Study Protocol

Determine the extent to which web-based cLEAR auditory brain training with concomitant support from a cLEAR in-house audiologist affects satisfaction with new hearing aids and increases daily use time.

B Background

B1 Prior Literature and Studies

clEAR auditory brain training has been shown to be effective and that patients like the contact with an audiologist during training. Barcroft et al. (2011; see also [name] et al., 2017) showed that computerized, game-like auditory training is beneficial for older adults (mean age=66 years, SD=16) who have hearing loss by conducting a 3-year large-scale study that addressed the effectiveness of computerized training for a talker trained with and for a talker not trained with. We also considered whether benefits were maintained three months later. A one-way ANOVA revealed a significant overall effect of training regardless of the talker. In a second study, Adults with hearing loss completed the clEAR program and were placed in a group that trained on either multiple talkers or a single talker (Barcroft et al., 2016). A control group also completed 12 hours of training in American Sign Language. The experimental group's training included a 4-choice discrimination task but not an open-set sentence test. The assessment phase included the same 4-Improvement on 4-choice discrimination was

observed in the experimental group as compared with the control group. Gains were (a) highest when the task and talker were the same between training and assessment; (b) second highest when the task was the same but the talker only partially so; and (c) third highest when task and talker were different. The findings support applications of transfer-appropriate processing to auditory training and favor tailoring programs toward the specific needs of the individuals being trained for tasks, talkers, and perhaps, for stimuli, in addition to other factors.

Patients want regular contact with an audiologist. In a study of 93 adults (mean age=66 years, SD=17), we asked the question, what did you like best about the auditory training ([name] et al., 2012). One of the three top answers was "regular contact with an audiologist". The other two were "the games were fun to play" and "training gave me empowerment over my hearing loss." By completing auditory brain training, participants also reported increased confidence to engage in everyday conversations.

C Study Objectives

C1 Primary Aim

It is the objective of this study to determine if the use of cLEAR following a first-time hearing aid fitting will increase satisfaction and daily hearing aid use.

C2 Secondary Aim

N/A

C3 Rationale for the Selection of Outcome Measures

1. Primary outcome measures are questionnaires used in hearing clinics to assess hearing aid satisfaction.
2. Hearing aids log use time. This information will also be collected to determine the average daily use time for each participant.

D Investigational Agent

D1 Preclinical Data

N/A

D2 Clinical Data to Date

N/A

D3 Dose Rationale and Risk/Benefits

N/A

E Study Design

E1 Overview or Design Summary

All qualified participants will first be fitted with one hearing aid using manufacturer recommended settings. The settings will be verified using real-ear measurements and any initial adjustments to the hearing aid will be made at the time of fitting. The participants will return again in 2-3 weeks to complete any final adjustments needed before they continue with the protocol.

After fitting and final adjustments are complete, all participants will be receive aided speech perception testing using the Speech in Noise Test (SPIN) and the NU-6.

Half of the participants will be assigned to the Early Group and receive 8 hours of cLEAR auditory brain training in 20 minute intervals spread over four weeks. The other half will be assigned to the Late Group and receive the cLEAR training after

a four week control period. The Early Group will do the control period after their training period.

For the control period, participants will be given a choice of three audio books stored on Amazon Kindle (a mystery, a biography, or a popular fiction) to ensure that the book will engage a participant's interest and that they will be motivated to follow the training schedule. They will be provided with a formal schedule that parallels the training schedule for the cLEAR training, and will receive 8 hours of training. We will confirm their compliance through weekly phone calls, email, and by asking them to report how far along they are in the book. If participants do not have a tablet for reading, they will be provided with a loaner tablet which allow access to Kindle books. A final period will be four weeks after either type of intervention.

At the end of each period participants will receive the speech perception battery (SPIN and NU-6) and the subjective assessment battery. The subjective assessment battery includes questionnaires and scales commonly used to assess hearing aid satisfaction and changes in listening challenges. The battery will include three subjective measures, The SADL (Satisfaction with Amplification in Daily Life), the IOI-HA (The International Outcome Inventory for Hearing Aids, and the COSI (Client Oriented Scale of Improvement). Finally, at the end of the cLEAR training period participants will complete a questionnaire designed to gain feedback about the games, participants will also complete a questionnaire about their cLEAR experience, indicating what they did and did not like about the system.

E2 Subject Selection and Withdrawal

2.a Inclusion Criteria

All participants have the same inclusion/exclusion criteria but be assigned to one of two groups that differ only in the schedule, this will allow participants will act as their own control group.

All participants will:

1. Be over 60 years old
2. Have a bilateral sensorineural hearing loss mild-to-severe range
3. Vision will need to be corrected to at least 20/40 so participants can see the training games on the computer or tablet monitor.

2.a Exclusion Criteria

English must be the first language of the participant

Participants must pass a dementia screener (MMSE)

Must have the manual dexterity to manipulate and insert a hearing aid

Must have an email address and access to the internet

2.b Ethical Considerations

Nobody will be discriminated against based on conditions not noted in the inclusion/exclusion criteria.

2.c Subject Recruitment Plans and Consent Process

Lists of potential participants will be obtained from multiple sources including the Washington University's Volunteers for Health program and from an extensive database maintained in the [name] lab. Potential participants will hear about the study and complete a health and hearing screening questionnaire over the telephone. If they pass the telephone screening, they will be asked to come to the hearing lab for the hearing and vision assessment. The hearing screening will include pure-tone threshold testing and speech perception testing at comfortable levels.

To be enrolled in the study potential participants will have bilateral mild to severe sensori-neural hearing loss, and have never used hearing aids. They will also require the basic skills for wearing and maintaining a hearing aid including the manual dexterity to insert the aid and the anatomy required to wear the aid. They will also have corrected static visual acuity of 20/40 or better. They will be required to pass a dementia screener (MMSE). If they qualify for the study and wish to continue they will be consented after completing the assessments. Those that do not qualify will be paid for their time and any collected data destroyed.

2.d Randomization Method and Blinding

Because participants act as their own control per se, they will not be randomized and no blinding will occur.

2.e Risks and Benefits

There are no foreseeable risks to the participant beyond the basic risks associated with hearing aid fitting. These risks are rare but include possible skin irritation from the device or the occasional uncomfortably loud sound. Hearing aids are equipped with safety mechanisms that are supposed to reduce the possibility that a very uncomfortable level is produced.

The participant will participate in a study that provides amplification and auditory training. These devices and procedures are designed to be of benefit to individuals with hearing loss. The participants will also be providing feedback on their experiences. This feedback may improve the procedures and methods currently used in online auditory training practices, this may benefit society.

2.f Early Withdrawal of Subjects

Participants that have not completed the study but can no longer participate will be asked to return the hearing aid. They will be reimbursed for their time at 10\$/hour.

2.g When and How to Withdraw Subjects

If it is deemed that they can no longer fulfill the needs of the study because they are not training or coming to the in-clinic assessments participants will be notified by phone or email if they are to be withdrawn from the study.

2.h Data Collection and Follow-up for Withdrawn Subjects

There will be no follow-up with withdrawn participants.

E3 Study Drug

3.a Description

N/A

3.b Treatment Regimen

N/A

3.c Method for Assigning Subjects to Treatment Groups

N/A

3.d Preparation and Administration of Study Drug

N/A

3.e Subject Compliance Monitoring

N/A

3.f Prior and Concomitant Therapy

N/A

3.g Packaging

N/A

3.h Blinding of Study Drug

N/A

3.i Receiving, Storage, Dispensing and Return

N/A

F Study Procedures

F1 Screening for Eligibility

A telephone survey will screen all potential participants that would not be eligible for reasons other than the hearing and vision screening. Hearing and vision testing will be conducted after the informed consent process.

F2 Schedule of Measurements

F3 Visit 1

F4 Visit 2 etc.

F5 Safety and Adverse Events

5.a Safety and Compliance Monitoring

5.b Medical Monitoring

- i **Investigator only**
- ii **Independent expert to monitor**
- iii **Institutional Data and Safety Monitoring Board**
- iv **Independent Data and Safety Monitoring Board**

5.c Definitions of Adverse Events

5.d Classification of Events

- i **Relationship**
- ii **Severity**
- iii **Expectedness**

5.e Data Collection Procedures for Adverse Events

5.f Reporting Procedures

5.g Adverse Event Reporting Period

5.h Post-study Adverse Event

F6 Study Outcome Measurements and Ascertainment

G Statistical Plan

G1 Sample Size Determination and Power

We determined the power to detect an effect size for differences as large as or larger than in [name] et al. (mean = .733, SD = .783) with an alpha level of .05 will exceed .95 using a one-tailed test for the within-subjects comparisons in each group.

G2 Interim Monitoring and Early Stopping

We will monitor progress in the software to be sure participants are following protocol.

G3 Analysis Plan

We will assess the effect of training on hearing aid use time, changes in speech perception, and subjective changes indicated by the questionnaire rating-scale responses. Three post-fitting times will be assessed to look at the effects of CLEAR testing (Baseline/post-fitting, post-training, post control, and four weeks post intervention).

G4 Statistical Methods

Data will be analyzed with t-tests and repeated measures ANOVA.

G5 Missing Outcome Data

Participants with missing data will not be included in the analyses for that outcome measure.

G6 Unblinding Procedures

N/A

H Data Handling and Record Keeping

H1 Confidentiality and Security

H2 Training

H3 Case Report Forms and Source Documents

H4 Records Retention

H5 Performance Monitoring

I Study Monitoring, Auditing, and Inspecting

I1 Study Monitoring Plan

I2 Auditing and Inspecting

J Study Administration

J1 Organization and Participating Centers

J2 Funding Source and Conflicts of Interest

INCLUDE INFO FROM CIRC? BUT WE ARE NOT THE PI, SO IT WOULDN'T MAKE SENSE HERE.

J3 Committees

J4 Subject Stipends or Payments

Participants will be paid \$10/hour for the time spent in assessments and training.

Other - The project involves first time hearing aid users. We need to control for the level of technology and hearing aid quality across participants, so the hearing aid will be provided. The aid will be 'used' after the study so the participant will be allowed to keep the aid after the study is complete.

J5 Study Timetable

K Publication Plan

L Attachments

L1 Tables

L2 Informed consent documents

Adult SBIR HA and AT Informed consent.rtf	Consent & Assent Forms	1	407 k	E	08/20/19
--	------------------------	---	-------	---	----------

L3 Patient education brochures

L4 Special procedures protocols

L5 Questionnaires or surveys

Attachment Name	Category	Ver	Size		Attached
JIT Letter.doc	Notice of Just in Time (JIT) Documentation	1	25 k	E	08/15/19
Telephone	Recruitment Script: Phone	1	59 k	E	08/19/19

Questionnaire.rtf					
AT and HA Flier.rtf	Recruitment Materials: Ads/Brochures/Posters/News Release/Fliers	1	115 k	E	08/19/19
COSI.pdf	Subject Data Collection Instruments	1	36 k	E	08/21/19
Demographic - Case History Form.rtf	Subject Data Collection Instruments	1	86 k	E	08/20/19
Email and Phone Script for Followups.doc	Subject Data Collection Instruments	1	23 k	E	08/20/19
IOI-HA.pdf	Subject Data Collection Instruments	1	37 k	E	08/21/19
SADL Form.pdf	Subject Data Collection Instruments	1	58 k	E	08/21/19
Assurance Form Signed.pdf	Assurance Document	1	226 k	E	08/21/19

M References

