“AUDITORY BRAIN TRAINING TO ENHANCE SATISFACTION AND USAGE OF NEW HEARING AIDS BY OLDER ADULTS”

NCT04230876

Document Date/Version: 6/15/22

Data will be analyzed with Repeated measures ANOVA to assess the effect of training on use time, changes in speech perception, and subjective changes indicated by the questionnaire rating-scale responses. Repeated measures will compare changes in outcome measures for the time spent during training to changes during the time spent not in the training. The numbers of participants in each group was determined based on effect sizes for the COSI in [name] et al. (2016), who found differences post-training using the same primary outcome measure, a similar training schedule and similar methods proposed here. We determined the power to detect an effect size for differences as large as or larger than in [name] et al. (mean = .733, SD = .783) with an alpha level of .05 will approach .95 using a one-tailed test for the within-subjects comparisons.

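### Protocol and SAP disagree on the primary outcome and neither says what counts as success; if any of three questionnaires may carry the claim, the false-positive chance can reach 14% rather than 5%

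*Protocol*

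**What the plan says.** **Primary outcome, protocol.** C3 states: "Primary outcome measures are questionnaires used in hearing clinics to assess hearing aid satisfaction". It does not say which. Logged use time follows as a separate list item without a rank. E1 gives the count: "The battery will include three subjective measures", namely SADL, IOI-HA and COSI.

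**Primary hypothesis, protocol.** A2 says that training "improves satisfaction with new hearing aids and increases daily use time". C1 repeats both components. C2 gives no secondary aim, so there is no lower tier.

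**Primary outcome, SAP.** Group sizes rest on the COSI effect in a cited 2016 study, which the SAP says "found differences post-training using the same primary outcome measure". Here the measure is singular.

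**Analysis.** G3 and the SAP list use time, speech perception and questionnaire responses side by side. G4 names t-tests and repeated measures ANOVA; the SAP names only the latter. No alpha, sidedness, order, adjustment or success rule is attached to these analyses.

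**Alpha.** The level appears only in the sizing text. G1 says power "with an alpha level of .05 will exceed .95 using a one-tailed test for the within-subjects comparisons in each group". The SAP says power "with an alpha level of .05 will approach .95 using a one-tailed test for the within-subjects comparisons", without the reference to each group.

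**The concern.** Two analysts could each follow a governing document and report different primary results. One, following C3, could present a positive SADL, IOI-HA or COSI result as support for the hypothesis. The other, following the SAP's sizing text, would look to COSI. The sizing sentence does not settle the matter: it explains how the number of participants was chosen, and it leaves C3, A2 and C1 as they are.

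What is at stake is the error rate of the trial's main claim. If the claim may rest on whichever of several measures turns out favourable, its false-positive chance is higher than the level of each test. Section 2.d says there is neither randomization nor blinding, and the questionnaires are self-reported, so a fixed primary outcome is one of the few protections against a selective claim.

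**Working it through.** **Inputs.** Planning difference "mean = .733, SD = .783" (G1 and SAP); alpha .05, one-tailed (sizing text only); 30 participants (A1), half in each group (E1), so 15 per group; three questionnaires (E1); use time as a fourth candidate (A2, C1). The documents give no correlation between outcomes, so the correlations below are assumptions.

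**1. The plan's own power figure.** Standardised difference d = .733/.783 = .936. For a one-tailed paired t-test with n = 15, the noncentrality is .936 × √15 = 3.63 and power is .964. This agrees with the protocol's figure for each group and is close to the SAP's. With all 30 pooled, power would be .9996, so the stated figure fits 15 per group.

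**2. Independent tests, any one sufficient.** The chance of at least one false positive among k tests at .05 is 1 − .95^k.
- Three questionnaires: 1 − .95³ = .143
- Three questionnaires plus use time: 1 − .95⁴ = .185

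**3. Correlated tests.** Simulation of k equally correlated one-sided t-tests, 100,000 runs per setting, gave:

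| Assumed correlation | k = 3, n = 15 | k = 3, n = 30 | k = 4, n = 15 | k = 4, n = 30 |
|---|---|---|---|---|
| .3 | .131 | .132 | .165 | .163 |
| .5 | .121 | .121 | .146 | .144 |
| .7 | .105 | .104 | .123 | .121 |
| .9 | .083 | .080 | .089 | .088 |

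Every entry exceeds .05.

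**4. If A2 requires both components.** Use time then adds no inflation, because it must also succeed. The choice among three questionnaires remains. If use time truly improves and satisfaction does not, a false satisfaction claim still has a chance of up to .143.

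**5. Sidedness.** If the analyses are two-sided at .05 and only favourable results count, each test has a false-positive chance of .025. Three independent tests then give 1 − .975³ = .073. The level is lower, but the inflation remains.

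**6. Power under the possible remedies**, at d = .936:

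| One-tailed alpha | n = 15 | n = 30 pooled |
|---|---|---|
| .05 (COSI alone) | .964 | .9996 |
| .05/3 = .0167 (first Holm step, three questionnaires) | .884 | .997 |

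The pooled column assumes that the planning effect size carries over to the training-versus-control contrast.

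**The case against.** The strongest reply is that the documents do not adopt an any-one-wins rule. A2 and C1 join satisfaction and use time with *and*, and C3 lists use time apart from the item it labels primary. The SAP's singular wording points to COSI. A1 also describes the aim in terms of feasibility and clinical utility, in 30 participants, where strict familywise control is less pressing. All of this is fair. It limits the size of the problem but does not remove it: no success rule is stated, and C3 still makes several questionnaires primary.

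Three stronger readings are tempting, and the documents do not support them.
- A reader might infer that every outcome will be tested at one-tailed .05. That level is given only for sizing; the analysis text gives none, and an ANOVA F-test is not one-tailed.
- A reader might count SPIN and NU-6 and arrive at 1 − .95⁶ = .265. No section calls the speech tests primary, and A2, C1 and C3 do not mention speech perception, so a positive speech result could not support the stated hypothesis.
- A reader might multiply the tests by the two groups. Only G1's power sentence refers to each group; the SAP drops the phrase and compares change during training with change outside it. Neither document plans a separate set of tests per group.

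A power argument for COSI alone is also weak if all 30 are pooled, since Holm would then leave first-step power at about .997.

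**Conclusion.** The point holds as a conflict between the documents, with inflation of uncertain size. The primary outcome is plural in the protocol and singular in the SAP, use time sits in the primary hypothesis without a rank, and nothing says which result would support the claim.

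If any one questionnaire at .05 suffices, the false-positive chance is at most about 14%, and about 8 to 13% at correlations of .9 to .3. If use time alone also suffices, it is at most about 19%, and about 9 to 16% at those correlations. The upper figures assume independent tests, which is unlikely for questionnaires answered by the same people. All the figures assume an any-one-wins rule, which the plan permits but does not state. They are bounds under stated assumptions, not the trial's known error rate.

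This should be corrected, because it decides which result the trial may present as confirming its hypothesis.

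**What to change.** In C3, G3 and the SAP:
- Name one primary outcome and contrast: COSI, change in the training period versus change in the control period. COSI is the only measure sized, and the contrast is already the SAP's own comparison. Give the time points that define each change.
- State the alpha and sidedness of the analysis, not only of the power calculation, and align the two power statements.
- Test daily use time second, in fixed sequence, at the same alpha and only if COSI succeeds. This respects A2 and keeps the error rate across both at the nominal level.
- Make SADL, IOI-HA, SPIN and NU-6 secondary, without confirmatory claims.

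If the sponsor prefers to keep all three questionnaires primary, use Holm. At the planning effect size, first-step power is about .88 with 15 per group and about .997 with all 30 pooled.

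The cost is a few sentences in each document. The real downside concerns content: the hypothesis is about satisfaction, and SADL is the scale named for it. With COSI alone as primary, neither SADL nor IOI-HA could support the primary claim by itself. The sponsor should make that choice openly and before outcome data are examined.

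### The own-control argument in section 2.d does not justify leaving Early versus Late assignment unrandomised: change with time since a first fitting may differ between the groups, and half of that difference would be credited to training

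*Protocol*

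**What the plan says.** Section 2.d of the protocol states: "Because participants act as their own control per se, they will not be randomized and no blinding will occur". Section 2.a gives the same rationale, saying that participants will "be assigned to one of two groups that differ only in the schedule, this will allow participants will act as their own control group".

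The design nevertheless has two arms that differ in order. E1 says "Half of the participants will be assigned to the Early Group", who train straight away, while the Late Group trains only after a four-week audiobook control period. E1 adds "The Early Group will do the control period after their training period", and later "A final period will be four weeks after either type of intervention". E1, 2.a and 2.d do not say how a person is placed in one group or the other. Section 3.c, which is headed as the place for that rule, reads N/A.

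All participants are first-time users (2.c), and period 1 begins after a return visit 2-3 weeks after fitting (E1). The aid is supplied so that technology is alike across people (J4). Within that frame they can vary: the hearing criterion is "Have a bilateral sensorineural hearing loss mild-to-severe range", and 2.c says "Lists of potential participants will be obtained from multiple sources".

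G1 states power "using a one-tailed test for the within-subjects comparisons in each group". G4 names t-tests and repeated measures ANOVA. The SAP compares change during training with change outside it. Neither document states a period or sequence term.

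**The concern.** Acting as one's own control removes whatever is stable about a person. It does not remove what changes over the weeks of the study. People wearing an aid for the first time may become more satisfied, or wear it longer, simply because more time has passed. Within either group, training is tied to one calendar period, so that change and the training effect cannot be separated there. Across the two groups they can be separated, but only if both groups would have changed alike without training. Random assignment is what gives a design basis for expecting this, and section 2.d gives it up for a reason that does not bear on the problem.

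The stake is the primary hypothesis in A2. It is causal: training improves satisfaction and increases use time. A1's talk of feasibility does not alter that. Device-logged use time avoids self-report, but it too can change with time since fitting.

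**Working it through.** **1. The plan's own figure.** Inputs: mean .733 and SD .783 (G1 and SAP), alpha .05 one-sided, n = 30/2 = 15 per group (A1). Standardised effect .733/.783 = .936. One-sample t-test power from the noncentral t with 14 df is .964. G1's claim of exceeding .95 reproduces. The sample-size arithmetic is not at issue, but it assumes no time trend within a group.

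**2. The bias.** Let τ be the training effect on change over a period. Let gE and gL be what each group's period 1 change minus period 2 change would be without training. Training minus control is then:

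- Early: τ + gE
- Late: τ − gL
- Equally weighted mean: τ + (gE − gL)/2

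If gE = gL, the trend cancels. A group difference that is equal in both periods also cancels, because it does not enter gE or gL. Only a difference in how the trend runs from period 1 to period 2 remains.

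**3. Its size, as illustration.** The documents give no trend sizes. I assume gE − gL of 0, .15 or .30, so the bias is 0, .075 or .150. The contrast SD is not given either. I take three values built on .783: a range, not a bound. No true effect, 15 per group, one-sided .05, 28 df, SE = SD/√30.

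| Contrast SD | Basis | SE | Rejection, bias .075 | Rejection, bias .150 | Power for .733, no bias |
|---|---|---|---|---|---|
| .783 | applied directly to the contrast | .143 | 12.9% | 26.7% | over 99% |
| 1.107 = .783√2 | independent period changes | .202 | 10.0% | 17.9% | 97.1% |
| 1.356 = .783√3 | successive changes share a measurement, independent errors | .248 | 8.9% | 14.6% | 89.3% |

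With zero bias, rejection is 5% in each row.

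**4. What period and sequence terms do.** Least squares on the six sequence-by-period cells, with sequence, period and training terms, weights Early +.5/−.5/0 and Late −.5/+.5/0. A common trend drops out, including over the final period; (gE − gL)/2 stays. Without those terms, and if the final period counts as time outside training, an assumed common trend of .30/.15/0 gives Early .30 − (.15 + 0)/2 = .225, Late .15 − (.30 + 0)/2 = 0, and a mean bias of .1125 even with identical groups. That is an analysis matter; randomising does not cure it.

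**5. Single-group tests.** Here the trend is not cancelled, and the result depends on what G1 compares.

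- Change in training against change in control, common g = .30: rejection 20-41% in Early, under 1% in Late.
- Pre-to-post training change, trend .30 then .15, SD .783: about 41% in Early, 17% in Late.
- End-of-period scores compared directly: continuing improvement lowers Early's contrast and raises Late's.

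**6. First-period Early-versus-Late change.** Assuming SD .783 applies to that change, SE = .783√(2/15) = .286. With 28 df, power for .733 is .804 one-sided and .697 two-sided. Without randomisation this comparison carries the whole group difference in first-period adaptation. A .30 difference equal in both periods gives 27% rejection here, against 5% in the pooled contrast.

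**The case against.** The strongest reply is that the design already deals with most of this. The two orders are opposite and of equal planned size, so a common trend cancels in the equally weighted two-period contrast. Identical criteria, first-time use, the same technology and the 2-3 week adjustment all narrow the scope for groups to adapt differently. A wide range of hearing loss and several recruitment sources show variation among people, not imbalance between groups. All of this stands. It limits the problem to gE − gL, but does not set that quantity to zero, and nothing in the documents makes assignment independent of severity or source.

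It is also fair that repeated measures ANOVA could contain period terms and that G3 lists several time points. The right statement is that such terms are not stated, not that they are ruled out.

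A reader might infer that staff will place people selectively, or that time since fitting confounds the whole trial. The documents support neither. They describe no selective assignment, and the second reading ignores the counterbalancing. Nor are the rejection rates above estimates of this trial's error rate: they follow from assumed trends.

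**Conclusion.** The concern holds in limited form. The stated reason for not randomising is invalid, and no rule protects assignment to the two sequences. What is exposed is a bias of (gE − gL)/2 in the two-sequence contrast, of unknown size and direction. For assumed differences of .15 and .30, one-sided rejection with no true effect is 9-13% and 15-27%; at zero difference it is the nominal 5%.

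This rests on contrast SDs of .783 to 1.356, on 15 per group, and on training having no after-effect on change in the next period. Under the SAP's change-based contrast, gains that are simply retained do no harm; fading or further growth after training would.

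The final-period question and the single-group tests are related weaknesses in how the analysis is specified. A reader might add them to the cost of not randomising, but randomisation would not remove them.

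**What to change.** **Assignment (2.d and 3.c).** For participants not yet assigned, randomise 1:1 to Early or Late after baseline testing, from a computer-generated permuted-block list that is concealed until baseline is recorded. Delete the own-control justification. This makes gE and gL equal in expectation.

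**Analysis (G4 and SAP).** Base the conclusion on the two-sequence contrast with period and sequence terms. Say whether the final period counts as time outside training, and if so let the terms cover it. Do not rest the conclusion on single-group tests.

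**Reporting.** Give the first-period Early-versus-Late change as supportive, and only for randomised participants. For anyone assigned without randomisation, attach the caveat that it carries the full group difference in adaptation, report how assignment was made, and limit causal claims.

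**Cost.** A short amendment and a randomisation list, with no extra participants or visits; everyone still receives both conditions. The first-period comparison has about 80% one-sided power for .733, below the planned .95. The period-adjusted pooled contrast keeps about 89% to over 99%. The documents do not give enrolment status; if assignment is complete, only the analysis and reporting changes remain available.
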